1. Do PLWHIV have a more severe disease course and outcomes from MPX as compared to MPX in PrEP user?
2. Are there particular factors, (e.g. CD4 T-cell nadir, current CD4 T-cell count, co-morbidities) within the group of PLWHIV, which put them at risk for a more severe MPX disease course?

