3 OBJECTIVES AND OUTCOME MEASURES/ENDPOINTS

It is hypothesised that HIV infection could be a risk factor for more severe MPX outcomes and that advanced immunodeficiency as defined by current CD4 T-cell count or CD4 T-cell nadir is a risk factor for more severe MPX outcomes in PLWHIV.

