3.1 Primary objective

1. To describe and compare outcomes of MPX in People Living with HIV (PLWHIV) and a HIV-negative population of people using pre-exposure HIV prophylaxis (PrEP users)
2. To identify risk factors for specific MPX outcomes (including CD4 cell count nadir and current CD4 count in PLWHIV)

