3.3 Primary endpoint/outcome

- Severity of lesions, clinical complications, percentage of hospitalizations*, death.
- Differences in the clinical manifestation of MPX in PLWHIV and PrEP users
- Differences in the clinical manifestation of MPX in PLWHIV by CD4 and VL.

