7.4 Primary outcome analysis

The first primary outcome analysis will be to describe outcomes of MPX in PLWHIV and in PrEP users in terms of severity of lesions, time to lesion resolution, hospitalization, death.

The rate of serious lesions will be estimated by dividing the number of participants with serious lesions by the total number of participants in the full analysis population. Unadjusted and adjusted odds ratios (ORs) will be calculated using the logistic regression model to assess the impact of HIV on the occurrence of serious lesions compared to PrEP users.

Because some participants' lesion may not be healed by the end of the study period and, therefore, the duration of resolution would not be known, and thus right-censored, survival analysis methods such as the Kaplan-Meier and Cox model will be used to assess the time to lesion resolution. Kaplan-Meier estimates will be used to estimate the median time to lesion resolution. Unadjusted and adjusted hazard ratios (HR) will be estimated using the Cox proportional hazard model to assess the impact of HIV-infection on the time to lesion resolution compared with PrEP users.

The hospitalization rate will be estimated by dividing the number of participants hospitalized for mpox infection by the total number of participants in the total analysis population. Unadjusted and adjusted odds ratios (ORs) will be calculated using the logistic regression model to compare hospitalization rates between PLWHIV and PrEP users.

The mortality rate will be estimated using the Kaplan-Meier Method. Unadjusted and adjusted hazard ratios (HR) will be calculated using the Cox proportional hazard model to compare the rates of mortality between PLWHIV and PrEP users.

Adjustment variables will include the following potential confounders: Age (<30 vs 30-40 vs >40 years); Sex at birth (female vs male); Comorbidities; multiple sexual partners (yes vs no); number of sexual partners in the last 3 months prior to mpox diagnosis; and smallpox vaccination history (yes vs no).

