The second primary outcome analysis will be performed between PLWHIV with MPX versus PrEP users with MPX. The endpoint is to assess differences in clinical manifestations of MPX between the groups. Unadjusted and adjusted odds ratios (ORs) will be calculated using the logistic regression models to compare the rates of clinical manifestations between PLWHIH and PrEP users. The adjusted variables will be the following (potential confounders): Age (<30 vs 30-40 vs >40 years); Sex at birth (female vs male); Comorbidities; multiple sexual partners (yes vs no); number of sexual partners in the last 3 months prior to MPX diagnosis; and smallpox vaccination history (yes vs no).

The third primary outcome analysis will be performed within the PLWHIV group. The endpoint is to evaluate the characteristics of HIV infection associated with severe mpox. Univariable and multivariable logistic regression models will be used to assess factors associated with severe mpox in PLWHIV. The following variables will be evaluated: time since HIV diagnosis (years); current ART; CDC disease stage; CD4 cell nadir; last CD4 cell count/HIV-RNA before MPX diagnosis (including CD4% and CD4/CD8 ratio). Variables achieving $P < 0.20$ in the univariable analysis will be retained for the multivariable analysis.

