7.5 Secondary outcome analysis

All secondary outcome analysis will be performed on PLWHIV with MPX compared to PrEP users with MPX.

The prevalence of MPX per site during the study period will be estimated by the number of MPX patients attending the site divided by the total number of patients the sites saw during the study period. The 95%

Confidence Interval of the prevalence will be calculated with the exact Clopper-Pearson method. Fisher exact test will be used to compare the prevalence of MPX in HIV-infected individuals to that of PrEP users.

The length of stay in hospital will be estimated using competing risk models with death as a competing event. Gray's test will be used to compare the duration of hospitalisation between PLWHIV and PrEP users. Unadjusted and adjusted sub-distribution hazard ratios (sHR) will be calculated using competing risk models with death as a competing event. The duration of hospitalization will be defined by the time (days) from hospitalization to hospital discharge or last observation. Adjustment variables will include: Age (<30 vs 30-40 vs >40 years); Sex at birth (female vs male); Comorbidities; multiple sexual partners (yes vs no); number of sexual partners in the last 3 months prior to mpox diagnosis; and Orthopoxvirus vaccination history (yes vs no).

Subgroup analyses for clinical manifestation in MPX will be conducted to assess the difference between PLWHIV and PrEP users across comorbidities. The following comorbidities will be assessed: diabetes mellitus, immunosuppression (e.g. solid organ transplant), chronic kidney or liver disease, mental health illness. Adjusted odds ratio will be calculated to compare PLWHIV and PrEP users within subgroup using logistic regression models. Adjustment variables will include: Age (<30 vs 30-40 vs >40 years); Sex at birth (female vs male); multiple sexual partners (yes vs no); number of sexual partners in the last 3 months prior to mpox diagnosis; and smallpox vaccination history (yes vs no).

Heterogeneity in the impact of HIV infection on clinical manifestations based on comorbidities will be assessed by including terms for interactions between patient status (PLWH and PrEP users) and the comorbidity variable in multivariable logistic regression models. All variables described above for adjustments will be included in the multivariable models.

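### Within PLWHIV, an unadjusted P<0.20 decides whether CD4 nadir and current CD4 get an adjusted estimate for severe mpox, and that model lists no age, co-morbidity or vaccination adjustment

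*Combined protocol and SAP*

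**What the plan says.** Section 3.1, primary objective 2: "To identify risk factors for specific MPX outcomes (including CD4 cell count nadir and current CD4 count in PLWHIV". The hypothesis in section 3 is more specific: "advanced immunodeficiency as defined by current CD4 T-cell count or CD4 T-cell nadir is a risk factor" for more severe outcomes in PLWHIV. Section 3.3 adds an endpoint worded for clinical manifestations: "Differences in the clinical manifestation of MPX in PLWHIV by CD4 and VL".

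The third primary analysis in section 7.4 serves these aims with univariable and multivariable logistic regression for severe mpox in PLWHIV. Its candidate list begins "The following variables will be evaluated: time since HIV diagnosis (years); current ART; CDC disease stage; CD4 cell nadir" and ends with last CD4 count and HIV-RNA, including CD4% and CD4/CD8 ratio. The entry rule is that variables with P<0.20 "in the univariable analysis will be retained for the multivariable analysis".

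For the first primary analysis, PLWHIV versus PrEP users, section 7.4 says "Adjustment variables will include the following potential confounders" and lists age, sex at birth, co-morbidities, sexual partners and smallpox vaccination. The second analysis has the same set. The third has none.

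Central question 2 in the Rationale asks: "Are there particular factors, (e.g. CD4 T-cell nadir, current CD4 T-cell count, co-morbidities) within the group of PLWHIV", which might put them at risk of a more severe course.

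**The concern.** A P<0.20 screen is common when the aim is to sift many candidate factors. Here two of the candidates are exposures named in advance, in a primary objective and in the hypothesis. For these, whether an adjusted estimate exists should not depend on the unadjusted result.

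A CD4 term that passes is adjusted only for the other HIV variables that also passed. If low CD4 goes with older age, more co-morbidity or a different vaccination history, the reader cannot tell how much of the association those account for.

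A lesser gap is that co-morbidities, an example factor in central question 2, get no planned estimate against severe mpox within PLWHIV.

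**Working it through.** **Text check.**

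1. Does anything exempt the CD4 factors from the screen? No. The entry rule follows the full candidate list and names no forced variable.
2. Does an adjustment set from elsewhere carry over? No. The lists in section 7.4 belong to the first and second analyses, both PLWHIV versus PrEP. Section 7.5 says that all variables described for adjustment enter the multivariable models, but that sentence closes the paragraph beginning "Heterogeneity in the impact of HIV infection on clinical manifestations based on comorbidities will be assessed by including terms for interactions". Section 7.5 is limited to PLWHIV-versus-PrEP comparisons.
3. Does that interaction model cover co-morbidities? Only in part. Its outcome is clinical manifestations, its target is the HIV effect, and no within-PLWHIV co-morbidity estimate is planned.
4. Are the variables collected? Section 6.2 lists age, co-morbidities and, if available, orthopoxvirus vaccination. For HIV it lists the last CD4 count but neither CD4 nadir nor CDC stage (Appendix 1 lists only AIDS).

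**How often could the screen remove a real effect?** The plan gives no power, effect size or event target for this analysis, so there is no figure to reproduce. What follows is an illustration.

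Inputs from the documents:
- 53 hospitalisations in 907 PLWHIV = 5.8% (section 6.1).
- 13% hospitalised in the cited early report (sections 1 and 2).

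Both stand in for severe mpox, which section 7.4 does not define.

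Assumptions: 1000 PLWHIV (the documents do not split the 2000), 25% in a low-CD4 group, no confounding.

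Method:
- Solve for the group risks p0 and p1 so that 0.75·p0 + 0.25·p1 equals the event rate and p1/(1−p1) = OR·p0/(1−p0).
- SE(log OR) = √(1/a + 1/b + 1/c + 1/d), using the four expected cell counts.
- With m = ln(OR)/SE, the chance of failing the two-sided P<0.20 screen is Φ(1.2816 − m) − Φ(−1.2816 − m).

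First row worked: p0 = 5.24% and p1 = 7.66%, so 39.3 events in 750 and 19.1 in 250. SE = √(1/19.1 + 1/230.9 + 1/39.3 + 1/710.7) = 0.289. Then m = 0.405/0.289 = 1.40, and Φ(−0.12) − Φ(−2.69) = 0.448.

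| Event rate | True OR | p0 | p1 | SE | m | Fails screen |
|---|---|---|---|---|---|---|
| 5.8% | 1.5 | 5.24% | 7.66% | 0.289 | 1.40 | 45% |
| 5.8% | 2.0 | 4.76% | 9.09% | 0.279 | 2.48 | 11% |
| 13% | 1.5 | 11.8% | 16.7% | 0.204 | 1.99 | 24% |
| 13% | 2.0 | 10.8% | 19.5% | 0.198 | 3.50 | 1% |

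Sensitivity for OR 1.5 at event rates of 5.8% and 13%:
- 820 PLWHIV (the 41% HIV share of the cited report, applied to 2000): 50% and 30%.
- 600 PLWHIV: 57% and 40%.
- 1000 PLWHIV with 10% low CD4: 59% and 43%; with 50% low CD4: 42% and 20%.

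These are chances for one factor. If nadir and current CD4 have equal effects and their test statistics are correlated 0.4 to 0.8 (assumed), both fail in 26–34% and 10–16% for OR 1.5. For OR 2.0 the ranges are 3–7% and 0.1–0.5%.

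**The case against.** The strongest reply is that the illustration assumes no confounding. In that case the univariable odds ratio, which remains available, carries nearly the same information as the adjusted one, and a screened-out CD4 term costs little. Real harm needs confounding, and the documents say nothing about its direction or size. This stands. The percentages show how often the adjusted result would be absent, not how wrong a conclusion would be.

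It can also be said that the study is mainly descriptive (section 7.2) and that this analysis is framed around characteristics of HIV infection, so a list of HIV variables may be deliberate. That is fair as far as it goes. The plan calls age, co-morbidities and vaccination potential confounders of the HIV comparison, not of CD4 and severity. But it gives no reason for leaving them out, and a stated hypothesis about CD4 calls for more than an exploratory sift.

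The co-morbidity gap is weak on its own: co-morbidities stand in an example list in the Rationale and not in the hypothesis, the primary objective or the primary endpoint.

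A reader might infer that the CD4 estimates will be biased, or that the CD4 objective will probably go unanswered. The documents support neither. The bias cannot be signed or sized from them, every CD4 factor keeps a univariable estimate, and both factors failing is less likely than either one failing.

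**Conclusion.** The point holds as a gap in specification. Followed as written, the plan can leave an exposure named in the primary objective without an adjusted estimate, and any CD4 estimate that survives is unadjusted for age, co-morbidities and vaccination. This follows from the text and does not depend on the illustration.

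The practical size depends on the strength of the effect and the number of events. For a moderate effect with few events the adjusted result is often lost; for a strong effect with events at 13% it almost never is. All these figures rest on the assumed number of PLWHIV, the low-CD4 share and hospitalisation as the proxy outcome. The change should be made, but the gap does not invalidate the study. The missing within-PLWHIV co-morbidity estimate is a minor addition.

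**What to change.** - Drop the P<0.20 rule for the CD4 factors. Pre-specify two logistic models for severe mpox in PLWHIV, one with current CD4 and one with CD4 nadir, each reported whatever its P-value.
- Give both a fixed adjustment set: age, a pre-defined co-morbidity summary and vaccination history. Leave AIDS, which Appendix 1 lists, out of the summary because it overlaps with the exposure. Reporting the co-morbidity coefficient would also give central question 2 a result.
- If vaccination history exceeds the 20% missing limit in section 7.7, fit the main model without it, add a sensitivity analysis with it, and state that confounding by vaccination may remain.
- Decide on sex and partner number in advance, not by the event counts observed.
- Label time since HIV diagnosis, ART, CDC stage, HIV-RNA, CD4% and CD4/CD8 ratio as exploratory.
- For this analysis, define severe mpox so that immunocompromise is not itself a criterion. The UK definition in section 6.2 counts confirmed infection in immunocompromised people as severe whatever its course, so low CD4 could otherwise define the outcome.
- Confirm that CD4 nadir and CDC stage are captured, since section 6.2 lists neither.

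The cost is mainly SAP wording, and possibly an eCRF field. The statistical price is fewer events per parameter. With five parameters (CD4 1, age 2, co-morbidity 1, vaccination 1) and 1000 PLWHIV, this is 58.4/5 ≈ 12 at 5.8% and 130/5 = 26 at 13%. With 600 PLWHIV at 5.8% it is 35.1/5 ≈ 7. Penalised estimation is an option if events are that few.

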6.2 Data collection

Only real-world retrospective data will be used for this study. Patients who have had mpox and fulfil the entry criteria will be enrolled after 90 days from date of diagnosis to allow for follow up data to be collected. Pseudonymised retrospective data will be transcribed into the eCRF system from source data at each clinical site or from existing cohort databases, where appropriate. No personal identifiable data will be transmitted to NEAT ID. The data elements will be transcribed from source data according to the data collection list below. Mechanisms to ensure data quality and integrity will be deployed as per applicable standard operating procedures and in line with Good Documentation Practice (GDocP) and Good Pharmacoepidemiology Practice (GPP). Patients will be identified and documented by participating sites.

For all patients with MPX the following information will be collected where routinely available:

- Age (year of birth)
- Sex and gender identity
- Ethnicity (where available)
- HIV status
- HIV pre-exposure prophylaxis (PrEP) use
- Comorbidities and Medical history (diabetes mellitus, other immunosuppression (e.g. solid organ transplant), known chronic kidney or liver disease, mental health conditions)
- Recent sexual history (3 months) – number of recent partners
- Recent and/or concomitant sexually transmitted infections
- Orthopoxvirus vaccination history (if available)
- Symptom onset date (fever onset, lesion onset, rectal pain)

- Date of positive PCR test result (documented)
- MPX severity -Reported clinical signs and symptoms of mpox (e.g. rash, mouth lesions, rectal pain, breathlessness)
- Time to resolution of lesions, if known
- Mortality as a consequence of MPX including cause
- Hospitalisation for MPX and length of hospitalisation
- Drug treatment for MPX (Tecovirimat, other)
- Drug for complications associated with MPX (laxatives, antibiotics, analgesia)
- recent travel to/living in endemic country or country with outbreak
- contact with suspected, probable, or confirmed case (if known)
- contact with infected animal (if known)

For PLWHIV the following additional information will be collected:

- Date of HIV diagnosis
- Current Antiretroviral Therapy/Treatment (ART)
- If not on ART, reason for not being on ART
- Last CD4 cell count (including CD4% and CD4/CD8 ratio) and
- Last HIV-RNA before MPX diagnosis

Skin lesion at peak severity score:

- Not presenting with skin lesions (0 skin lesions)

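### CD4 nadir is required by primary objective 2 and the third primary analysis, but the section 6.2 data collection list does not include it

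*Combined protocol and SAP*

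**What the plan says.** Three places give CD4 nadir a role at the primary level.

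- The hypothesis in section 3 states that "advanced immunodeficiency as defined by current CD4 T-cell count or CD4 T-cell nadir is a risk factor" for worse outcomes in people living with HIV.
- Primary objective 2 in section 3.1, repeated in the synopsis, is "To identify risk factors for specific MPX outcomes (including CD4 cell count nadir and current CD4 count in PLWHIV").
- The third primary analysis in section 7.4 will evaluate "time since HIV diagnosis (years); current ART; CDC disease stage; CD4 cell nadir; last CD4 cell count/HIV-RNA before MPX diagnosis", with CD4% and CD4/CD8 ratio added to the last item.

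The second central question in section 2 also mentions nadir, but only as an example.

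On collection, section 6.2 says: "The data elements will be transcribed from source data according to the data collection list below". Under the line "For PLWHIV the following additional information will be collected" it gives five items: date of HIV diagnosis, current ART, the reason if not on ART, "Last CD4 cell count (including CD4% and CD4/CD8 ratio) and" "Last HIV-RNA before MPX diagnosis".

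**The concern.** The objective and the analysis call for a variable that the collection list does not supply. The protocol treats nadir and current CD4 as separate markers: the hypothesis sets them as alternatives, the objective names both, and section 7.4 lists them as separate predictors. Having one does not cover the other.

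At stake is one named component of a primary objective. If sites abstract only what is listed, nobody can say at the end whether a low nadir is associated with severe mpox in this cohort. The loss might be noticed only at analysis, after abstraction has closed.

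**Working it through.** No arithmetic figure in the plan is in question. The check sets the variables of the third primary analysis against everything section 6.2 and Appendix 1 say will be collected.

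| Variable in section 7.4 | Source in section 6.2 or Appendix 1 |
|---|---|
| Time since HIV diagnosis | Derivable from HIV diagnosis date and PCR date |
| Current ART | Listed |
| CDC disease stage | Partial: Appendix 1 lists AIDS, with no definition and no stage |
| CD4 nadir | None |
| Last CD4 count | Listed |
| CD4% | Listed |
| CD4/CD8 ratio | Listed |
| Last HIV-RNA | Listed |

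Counted singly there are 8 variables: 6 have a source, 1 has a partial source (CDC stage) and 1 has none (nadir). Of the 5 items in the list for people living with HIV, 0 give nadir. The all-patient list and the lists of lesion severity, lesion site and complications do not give it either. Of the 2 CD4 markers named in primary objective 2, 1 (current count) is listed and 1 (nadir) is not.

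**Could text have been lost?** The CD4 item ends in a conjunction, but the next item, on HIV-RNA, completes it. There is no redaction mark at that point.

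**Can nadir be derived from what is listed?** The plan does not define nadir. I take it as the lowest count on record up to the mpox diagnosis. Then 0 ≤ nadir ≤ last count, so the last count gives an upper limit and no more. Two people with the same last count of 600 (an assumed value) could have nadirs anywhere from 0 to 600.

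**Can imputation supply it?** Section 7.7 excludes variables with more than 20% missing. A variable that is never collected is 100% missing. One supplied by only some sites could also pass 20%.

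**What is untouched?** The current-CD4 part of the hypothesis and of objective 2, the primary endpoint "Differences in the clinical manifestation of MPX in PLWHIV by CD4 and VL", and every comparison of people living with HIV against PrEP users.

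**The case against.** The strongest reply is that section 6.2 is not the full data dictionary. It names only a few comorbidities, while Appendix 1 defines many more. Section 3.4 counts only hospitalisations for clinical reasons, yet section 6.2 lists no reason for admission. Absence from the list is therefore weak evidence of absence from the eCRF, which the documents do not contain. Section 6.2 also allows transcription from existing cohort databases, which may hold nadir.

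This stands as a limit on certainty. A reader might infer that nadir is not being collected; the documents do not show that. They show that the protocol's own statement of what is transcribed leaves out something its primary objective needs. If the eCRF does hold nadir, the list is incomplete; if it does not, part of the objective cannot be met. Either way the sections need reconciling.

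A second reply is that the study is described as mainly descriptive, and that nadir is one candidate among several, reaching the multivariable model only if its univariable P is below 0.20. That limits the damage, but nadir is still named in a primary objective, and its univariable evaluation is planned regardless of that threshold.

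A third reply concerns the hypothesis. It joins current count and nadir with an 'or', so it can be tested in part with current CD4 alone. That is correct. The statements that clearly require nadir are primary objective 2 and the third primary analysis.

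**Conclusion.** The mismatch is real and should be fixed. If collection follows section 6.2, the nadir part of primary objective 2 and of the third primary analysis cannot be carried out. The size is one of the two CD4 markers named in the objective, and one of the eight predictors counted singly. The conclusion assumes that the list governs what is abstracted, as section 6.2 says, and that neither the eCRF nor the cohort databases already supply nadir. The documents cannot settle the second assumption.

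Two stronger readings go too far. One is that objective 2, the hypothesis or the third primary analysis fails as a whole; current CD4, HIV-RNA, ART and time since diagnosis all have a listed source. The other is that CDC stage has no source at all; the AIDS item in Appendix 1 is a partial one. What is missing there is the full stage named in section 7.4, and that is the lesser point.

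**What to change.** 1. Add CD4 nadir (value and date) to the section 6.2 list for people living with HIV. Before abstraction is completed, confirm that it is in the eCRF or in the cohort databases used. Section 9.2 limits collection to what the objectives need; objective 2 names nadir, so the addition is within that limit.
2. If nadir cannot be obtained, or is excluded under the 20% rule in section 7.7, keep the objective and the planned analysis as written and report nadir as not evaluable. It should not be dropped silently.
3. For CDC stage, either add it to the list or state that the AIDS item in Appendix 1 will be used in its place.

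The cost is two fields (nadir value and date), or three with CDC stage, for people living with HIV only. Nadir requires a review of each patient's CD4 history, not only the latest result, so the abstraction time is not trivial. The change may need review as an amendment under section 10.1. Collection is wholly retrospective, so no patient visit is needed. If the eCRF already holds the fields, only the protocol list needs correcting.

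### Section 7.4 will evaluate CDC disease stage and CD4 nadir as factors for severe mpox in people living with HIV, but the section 6.2 data collection list contains neither

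*Combined protocol and SAP*

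**What the plan says.** Section 7.4 sets out a third primary outcome analysis, confined to people living with HIV. It uses univariable and then multivariable logistic regression for severe mpox. The factors to be evaluated include "time since HIV diagnosis (years); current ART; CDC disease stage; CD4 cell nadir", followed by the last CD4 count (with CD4% and CD4/CD8 ratio) and HIV-RNA before mpox. Factors with P below 0.20 in the univariable step go forward to the multivariable model.

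Section 6.2 states how data reach the eCRF: "The data elements will be transcribed from source data according to the data collection list below". The HIV block of that list opens with "For PLWHIV the following additional information will be collected" and has five items: date of HIV diagnosis, current ART, the reason if not on ART, last CD4 count (with CD4% and CD4/CD8 ratio) and last HIV-RNA. The general list, for all patients, has a comorbidity item: "Comorbidities and Medical history (diabetes mellitus, other immunosuppression (e.g. solid organ transplant), known chronic kidney or liver disease, mental health conditions".

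Section 7.7 provides for multiple imputation and excludes variables with more than 20% missing.

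**The concern.** A factor can be screened and modelled only if someone records it. Section 7.4 promises an evaluation of CDC disease stage, yet the list that governs transcription has neither the stage nor the clinical history from which a stage could be assigned. CD4 nadir, in the same sentence of 7.4, has the same gap.

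If the plan is followed as written, pre-specified factors of a primary analysis drop out because no data exist, and not through the P < 0.20 screen or any stated decision. For stage, the loss is a record of past clinical HIV disease, which neither a current CD4 count nor a current viral load supplies directly. For nadir, the loss touches the study's stated purpose: section 3 defines advanced immunodeficiency by current CD4 or CD4 nadir, and primary objective 2 in section 3.1 names nadir explicitly.

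**Working it through.** No arithmetic beyond a count applies, and the plan gives no figure on this point to reproduce. The check is to match each factor in section 7.4 to a source in section 6.2.

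| Factor named in 7.4 | Source in 6.2 |
|---|---|
| Time since HIV diagnosis | Yes, derivable from "Date of HIV diagnosis" |
| Current ART | Yes, listed in the HIV block |
| CDC disease stage | None |
| CD4 nadir | None |
| Last CD4, CD4%, CD4/CD8 ratio | Yes: "Last CD4 cell count (including CD4% and CD4/CD8 ratio) and" |
| Last HIV-RNA | Yes: "Last HIV-RNA before MPX diagnosis" |

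Four of six factors have a source and two of six do not.

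Possible other sources for CDC stage:

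1. **The rest of section 6.2.** The comorbidity item names no AIDS diagnosis and no HIV stage. The lesion score, lesion sites and complications concern mpox itself. None helps.
2. **Appendix 1.** The comorbidity table has an AIDS row. Section 6.2 does not refer to the appendix. If the row is collected, it gives at most a yes/no and not a stage. Nothing in section 6.2 ties it to the period before mpox.
3. **Derivation.** The documents do not define CDC stage: there is no classification version, no time point and no rule that builds it from AIDS status and CD4. A stage assigned from the last CD4 alone would add little to the CD4 variable already in the model.
4. **Imputation.** A variable that is never recorded is missing for everyone. Under the 6.2 list that is 100%, against the 20% limit in section 7.7. This only restates the absence; it shows that imputation is not a way out.

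For CD4 nadir, no other section supplies a source, and nadir cannot be derived from a single last CD4 value.

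**The case against.** The strongest reply is that this is a small mismatch over one covariate. Several parts of that reply stand.

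- **The analysis survives.** A reader might infer that the third primary analysis cannot be run. The documents do not support that: four factors have sources, and 7.4 already allows any factor to drop out at the univariable screen. What cannot be run is the evaluation of all the named factors.
- **The hypothesis does not rest on CDC stage.** A reader might infer that losing stage undermines the central hypothesis. Section 3 defines advanced immunodeficiency by current CD4 or CD4 nadir. Stage also does not appear in the second central question (section 2), primary objective 2 (section 3.1) or the primary endpoints (section 3.3), which refer to CD4 and viral load.
- **Stage is not the only carrier of HIV history.** Time since diagnosis and current ART also describe HIV history beyond CD4 and viral load, and both are collected.
- **A partial source may exist.** The title of Appendix 1 and the Charlson indices in the abbreviations list suggest that its rows may be meant for collection. AIDS status with the last CD4 could feed a derived stage if a rule were written. The AIDS row shows no definition, but the table runs over a page and its definition column may not have carried across, so nothing should be made of that. The eCRF is not among the documents and may hold a field.

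These points limit the consequence but do not remove the gap. Section 6.2 presents its list as what is transcribed, and section 9.2 commits to the minimum data needed for the objectives, so a site has little basis for abstracting an unlisted stage. If the eCRF does hold the field, 6.2 and 7.4 still need to be reconciled. The reply also leaves CD4 nadir untouched.

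**Conclusion.** The point holds in a limited form. Two of the six factors named for the third primary analysis, CDC disease stage and CD4 nadir, have no source in section 6.2, and no rule derives stage from what is collected. The reduced analysis on time since HIV diagnosis, current ART, last CD4 (with CD4% and ratio) and last HIV-RNA remains feasible.

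Complete missingness is a statement about the 6.2 list only. It assumes that the list governs the eCRF, as section 6.2 says, and that the Appendix 1 AIDS row does not stand in for stage. It is not a finding about data actually held. Of the two gaps, nadir matters more, because the hypothesis and primary objective 2 name it. The stage gap alone would not invalidate the study, but it should be corrected because it sits in a primary analysis and is cheap to close.

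**What to change.** Amend the HIV block of section 6.2 and align section 7.4 with it:

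1. Add one of two items: CDC stage before the mpox PCR date, with the classification version stated; or AIDS-defining illness before the mpox PCR date (yes/no, with the date of the first). Use the chosen item in 7.4. The second option replaces the named factor, so 7.4 must be reworded to match. Fixing the time point before the PCR date ensures that the factor precedes the outcome.
2. Add CD4 nadir in the same amendment.
3. If sites cannot abstract stage or AIDS history, delete CDC disease stage from 7.4.

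The cost is an eCRF change, possibly with amendment review under section 10.1, and slightly more abstraction for each HIV case among the approximately 2000 records at up to 12 sites. Collection is retrospective and sites keep the link between identifier and patient (section 9.2), so cases already entered can be completed from existing records. Deleting the stage term costs only a change of text, but gives up that factor.
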